
Statistical methods
	
Treatment outcome:
 
Loco-regional control is defined as absence of loco-regional progression based on findings of endoscopy, endoscopic ultrasound, and computed tomography. OS, PFS, MFS and LC are calculated for both treatment groups and for several potential prognostic factors with the Kaplan-Meier method and measured from the day of randomization .
 
Such potential prognostic factors are: age (≤ 60 vs. > 60 years), Karnofsky performance status (100%-80% vs. 70%), tumor location (upper third vs. middle third vs. lower third), tumor length (< 7 cm vs. ≥ 7 cm, according to endoscopy), histology (squamous cell carcinoma vs. adenocarcinoma), histologic grade (G1-2 vs. G3), T-stage (T2-3 vs. T4, according to endoscopic ultrasound and computed tomography), N-Stage (N0 vs. N+), and hemoglobin before radiotherapy (< 12 vs. 12-14 vs. > 14 g/dl).
 
Differences between the Kaplan-Meier curves are evaluated with the log-rank test. Results are considered significant if $P < 0.05$. Potential prognostic factors found to be significant in the univariate analysis, are evaluated in a multivariate analysis performed with the Cox proportional hazard model.
 
Stratification at randomization according to :
 
Histology (SCC vs. adeno) KPS (100%-80% vs. 70%) Stage (T1-3 N0-1 vs. T4 and/or N2 and/or M1a)
 
Toxicity:
 
Both treatment groups are compared for toxicity using the Chi-square test.

-----------------------------------	---

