8.2.2 Secondary variables

- The 1-year overall survival
- The 1-year and 2- year progression-free survival
- The 1-year and 2-year loco-regional control
- The 1-year and 2-year metastases-free survival
- The overall response rate³ (RECIST Version 1.1)
- Toxicity (NCI-CTC 4.0)
- Quality of Life (EORTC QLQ-C30 and QLQ-OES18)

In addition the following parameters will be assessed irrespective of a specific time point:

- OS
- PFS
- MFS

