8.3 Statistical analysis

8.3.1 Statistical Methode

Treatment outcome:

Loco-regional control is defined as absence of loco-regional progression based on findings of endoscopy, endoscopic ultrasound, and computed tomography.

OS, PFS, MFS and LC are calculated for both treatment groups and for several potential prognostic factors with the Kaplan-Meier method and measured from the day of randomization .

Such potential prognostic factors are: age (≤ 60 vs. > 60 years), Karnofsky performance status (100%-80% vs. 70%), tumor location (upper third vs. middle third vs. lower third), tumor length (< 7 cm vs. ≥ 7 cm, according to endoscopy), histology (squamous cell carcinoma vs. adenocarcinoma), histologic grade (G1-2 vs. G3), T-stage (T2-3 vs. T4, according to endoscopic ultrasound and computed tomography), N-Stage (N0 vs. N+), and hemoglobin before radiotherapy (< 12 vs. 12-14 vs. > 14 g/dl).

Differences between the Kaplan-Meier curves are evaluated with the log-rank test. Results are considered significant if $P < 0.05$. Potential prognostic factors found to be significant in the univariate analysis, are evaluated in a multivariate analysis performed with the Cox proportional hazard model.

Stratification at randomization according to :

Histology (SCC vs. adeno)

KPS (100%-80% vs. 70%)

Stage (T1-3 N0-1 vs. T4 and/or N2 and/or M1a)

Toxicity:

Both treatment groups are compared for toxicity using the Chi-square test.

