8.3.2 Present therapeutic situation

The most effective radiochemotherapy regimens, containing 5-FU and cisplatin, achieve a overall survival (OS) rate of 36% to 40% after two years [49, 50, 52]. Thus, a 40% OS rate at 2 years is assumed as the baseline efficacy level for the present trial.

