8.3.4 Design and assumptions

- Explorative randomized phase II study with 2 parallel groups.
- Primary endpoint: Overall survival rate after 2 years. Survival time will be calculated from time of randomization until death for any reason, or until last date known to be alive, whichever occurs first. In patients without death, the last date known to be alive will be considered as censored survival time.
- The respective experimental therapy arm would be rated as insufficiently active, if the observed OS rate at 2 years is 40 % or lower, as this corresponds to the standard treatment efficacy.
- On the other hand, the experimental therapy would be considered to be a promising candidate for further development (e.g. in a phase III trial), if the true OS rate at 2 years amounted to 45% or more.

- In order to detect potential differences with respect to the investigated study endpoints between female and male gender, subgroup analyses will be performed for both female and male patients. Furthermore, the potential prognostic impact of gender will be analyzed in a univariate and a multivariate manner. Because an adequate statistical power cannot be expected in each of the two subgroups, the statistical evaluation analyses with respect to gender related differences will be presented in a descriptive manner.

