The 2-years overall survival rates will be estimated using Kaplan-Meier methods and the difference between treatment groups regarding 2-years overall survival curves will be compared using the log-rank test. In addition, univariate Cox proportional hazard methods will be used to estimate the corresponding hazard ratio (HR) and 95% confidence intervals for HR.

Based on the expected number of patients randomized until end of 2016, the following difference (hazard ratios) can be detected between the two treatment arms with 80% power and a two-sided significance level of 0.05, assuming that the 2-years OS probability is between 30 and 40%, and number of lost-to-follow-ups is about 5% during the 2 years.

Table 10: Hazard ratios and necessary numbers of events

Sample size	2-year OS probability		Necessary number of events	Hazard ratio
	CT only	CT plus Cetuximab		
2 x 33	30%	63.14	34	0.3820
	35%	68.38	31	0.3621
	40%	73.19	28	0.3407
2 x 36	30%	61.73	38	0.4007
	35%	67.02	35	0.3812
	40%	71.90	31	0.3601
2 x 39	30%	60.48	42	0.4177
	35%	65.81	38	0.3986
	40%	70.74	34	0.3778

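### Loco-regional control is estimated by Kaplan-Meier with loco-regional progression as its only event; this implies censoring of deaths, so the 1- and 2-year failure rates will be overstated to the extent that deaths come first.

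*Combined protocol and SAP*

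**What the plan says.** Section 8.3.1 gives the endpoint: "Loco-regional control is defined as absence of loco-regional progression based on findings of endoscopy, endoscopic ultrasound, and computed tomography". The next sentence gives the estimator, with time counted from randomization: "OS, PFS, MFS and LC are calculated for both treatment groups and for several potential prognostic factors with the Kaplan-Meier method". The test follows: "Differences between the Kaplan-Meier curves are evaluated with the log-rank test". The synopsis (Statistical methods) repeats this: "OS, PFS, MFS and LC are calculated for both treatment groups".

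Section 8.2.2 lists among the secondary variables "The 1-year and 2-year loco-regional control". The further list in that section, of parameters assessed without a fixed time point, holds OS, PFS and MFS but not LC. LC is therefore named only as two point rates.

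The only written censoring rule is in section 8.3.4 and concerns overall survival: "In patients without death, the last date known to be alive will be considered as censored survival time". There is none for LC. No competing-risk method appears anywhere in the document, and no event definition is given for PFS or MFS.

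On expected mortality, section 8.3.2 says: "Thus, a 40% OS rate at 2 years is assumed as the baseline efficacy level for the present trial". The revised power calculation in section 8.4 works with a range for the chemoradiotherapy-only arm: "assuming that the 2-years OS probability is between 30 and 40" per cent.

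**The concern.** If loco-regional progression is the only event, a patient who dies without it has no event and cannot stay under observation. In an ordinary Kaplan-Meier analysis that patient is censored at death. Kaplan-Meier then gives the patient the same future risk of loco-regional progression as those still alive. The result describes a hypothetical setting without death, not the share of randomized patients whose disease fails loco-regionally.

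Death is not rare here, and LC enters the plan only through the two point rates, which are the quantities affected. Readers will take a 2-year LC figure as the proportion of patients controlled. If mortality without loco-regional progression differs between arms, or between prognostic groups such as those defined by performance status or T-stage, the distortion differs too, and randomization does not cancel it.

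**Working it through.** **There is no plan figure to reproduce.** The documents state no expected LC rate, so only the direction follows from the text. The size needs assumptions.

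**Direction.** One minus Kaplan-Meier with deaths censored is never below the cumulative incidence of loco-regional failure. It is strictly above it once a death without loco-regional progression comes before a later loco-regional progression. This needs no model.

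**Bound from the documents.** Two-year OS of 40% (8.3.2) means 60% dead. The 30 to 40% range in 8.4 means 60 to 70% dead. Only deaths without prior loco-regional progression compete, so these are upper bounds on the competing event.

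**Size.** Assumed, not in the documents:
- constant cause-specific hazards;
- E, the proportion alive and free of loco-regional progression at 2 years: 25%, 30% or 40%;
- s, the share of first events that are loco-regional: 1/3, 1/2 or 2/3.

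Formulas:
- cumulative incidence = s × (1 − E)
- one minus Kaplan-Meier = 1 − E^s

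| E | s | Cumulative incidence | 1 − KM | Overstatement (points) |
|---|---|---|---|---|
| 25% | 1/3 | 25.0% | 37.0% | 12.0 |
| 25% | 1/2 | 37.5% | 50.0% | 12.5 |
| 25% | 2/3 | 50.0% | 60.3% | 10.3 |
| 30% | 1/3 | 23.3% | 33.1% | 9.7 |
| 30% | 1/2 | 35.0% | 45.2% | 10.2 |
| 30% | 2/3 | 46.7% | 55.2% | 8.5 |
| 40% | 1/3 | 20.0% | 26.3% | 6.3 |
| 40% | 1/2 | 30.0% | 36.8% | 6.8 |
| 40% | 2/3 | 40.0% | 45.7% | 5.7 |

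The range is 5.7 to 12.5 points. E cannot exceed OS. At 40% OS, the E = 40% rows require that no patient with loco-regional progression is alive at 2 years; at 30% OS they are impossible. The lower end is therefore the less plausible one for the control arm.

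**At 1 year**, for E = 30% at 2 years and s = 1/2: the event-free proportion is √0.30 = 54.8%. The cumulative incidence is 0.5 × 45.2% = 22.6%, and 1 − KM is 1 − √0.548 = 26.0%. The overstatement is about 3.4 points.

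**Second parameterization.** Fix OS at 40% and assume that half of the deaths (30% of patients) occur without prior loco-regional progression. For a true 2-year failure of 30%, 40% or 50%, 1 − KM gives 36.8%, 49.7% or 63.4%. The overstatement is 6.8, 9.7 or 13.4 points at 2 years, and 2.1, 3.3 or 5.0 points at 1 year. Letting the share of such deaths run from 25% to 75% and the true failure from 20% to 50%, wherever feasible, widens the 2-year range to 5.4 to 29.3 points.

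**Difference between arms.** Table 10 includes a row with 2-year OS of 40% against 73.19%. Assume, compatibly with that row, E = 30% against 60%, and s = 1/2 in both arms. Cumulative incidence is 35.0% against 20.0%, a difference of 15.0 points. 1 − KM is 45.2% against 1 − √0.60 = 22.5%, a difference of 22.7 points. The overstatement is 10.2 points in one arm and 2.5 in the other.

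**The case against.** The strongest case on the other side has five parts.

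1. **Censoring of deaths is not written.** A reader might infer that the plan prescribes it. It does not; 8.3.1 is silent and the only censoring rule is for OS. This stands as a limit on wording. It does not remove the problem, because the stated event and estimator leave no other ordinary reading.
2. **Total mortality is not the competing risk.** A reader might infer that 60 to 70% of control patients are wrongly censored. The documents do not support that. Patients who die after loco-regional progression already count as LC events, and the split is not given. This stands.
3. **The planned comparison is sound.** A reader might infer that the LC comparison between arms is invalid. It is not: the log-rank test remains a valid comparison of cause-specific hazards, and so does a Cox model labelled that way. What misleads is reading the 1- and 2-year Kaplan-Meier values, or their difference, as proportions of patients. A reading as control in the absence of death is possible, but the plan does not label it so, and it relies on death and loco-regional progression being independent, which the data cannot verify.
4. **Little turns on LC.** It is secondary in an explorative trial, and the final conclusion in 8.4 rests on the OS rate, the reference arm and toxicity. With 36 patients per arm, a 35% failure rate has a 95% half-width of about 1.96 × √(0.35 × 0.65 / 36) = 16 points, larger than the main range above. This limits the consequence. It does not excuse a systematic error of known direction, especially as 8.3.3 makes efficacy estimation the purpose of the trial.
5. **PFS and MFS.** A reader might assume that death counts as an event there, or that the same fault applies. The documents settle neither, since they define no event for either endpoint.

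**Conclusion.** The point holds for the 1- and 2-year LC rates. As defined and estimated, they imply censoring of patients who die without loco-regional progression, and they overstate actual loco-regional failure (understate actual control) to the extent that such deaths come first. The direction is certain whenever such deaths precede later progressions. The size cannot be derived from the documents: it is about 6 to 12.5 points at 2 years under constant hazards, 25 to 40% event-free, and one third to two thirds of first events loco-regional. Other assumptions give more. The bias can differ by arm if mortality differs. The log-rank and Cox comparison stays valid for cause-specific hazards, and the primary OS analysis is untouched. This should be corrected before analysis, but it does not threaten the trial's main conclusion.

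**What to change.** In section 8.3.1 and the synopsis:

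- State how death is handled for LC.
- Estimate 1- and 2-year loco-regional failure by the Aalen-Johansen cumulative incidence, by arm and by prognostic factor, with death without prior loco-regional progression as the competing event.
- Keep the log-rank and Cox analyses of LC, labelled as comparisons of cause-specific hazards.
- Keep Kaplan-Meier for OS. Keep it for PFS and MFS provided the plan confirms in the same edit that death is an event in each.

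The cost is a few sentences and a standard procedure. No new data are needed, because dates of death and of loco-regional progression are already required for OS and LC.

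### Age, tumour length and haemoglobin are tested for prognosis only as fixed groups, which may cost roughly 12-35 points of power for a moderate log-linear effect in an exploratory analysis

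*Combined protocol and SAP*

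**What the plan says.** Section 8.3.1 lists potential prognostic factors for OS, PFS, MFS and loco-regional control. Three of them are measured on a continuous scale and appear only in grouped form: "age (≤ 60 vs. > 60 years" for age, "tumor length (< 7 cm vs. ≥ 7 cm, according to endoscopy" for tumour length, and "hemoglobin before radiotherapy (< 12 vs. 12-14 vs. > 14 g/dl" for haemoglobin. The synopsis gives the same list.

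The test is stated as "Differences between the Kaplan-Meier curves are evaluated with the log-rank test", at P < 0.05. The entry rule for the adjusted model is: "Potential prognostic factors found to be significant in the univariate analysis, are evaluated in a multivariate analysis performed with the Cox proportional hazard model".

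No section gives a continuous analysis, a reason for the cut points, the expected distribution or effect of these factors, or the power of any prognostic test. Age is collected with the demographic data (Table 8), haematology within 7 days before treatment (Section 7.1.2), and endoscopy at screening (Section 7.1.1). Nothing in the text says whether tumour length is recorded in centimetres or only as a category.

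**The concern.** Cutting a continuous measure discards the ordering within each group. A patient aged 61 counts the same as one aged 80, and a 7 cm tumour the same as a 12 cm one. Haemoglobin, in three unordered groups, is tested on 2 degrees of freedom.

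The univariate test is also the gate to the multivariate model, so a factor that misses P < 0.05 because of grouping is missing from the adjusted model too. The trial is small: Section 8.4 expects 72-78 patients in the Full Analysis Set and 66-72 in the per-protocol set, and Section 8.1 makes the per-protocol set primary for efficacy. With so few deaths, information lost through coding is hard to spare.

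**Working it through.** **1. The plan's own figure.** The only power figures are in Table 10 (Section 8.4), for the treatment log-rank test "with 80% power and a two-sided significance level of 0.05". For 2 x 36 patients and 2-year OS of 30% versus 61.73%:

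- HR = ln(0.6173)/ln(0.30) = 0.4007, as stated.
- Schoenfeld events = 4 × (1.960 + 0.842)² / (ln 0.4007)² = 37.5, so 38, as stated.

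All nine rows reproduce to within one event (range 28-42). A two-sided 5% level is therefore assumed for the prognostic tests as well; Section 8.3.1 does not state sidedness.

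**2. Number of deaths.** If 2-year OS is 40% overall, deaths are about 0.60 × N: 39.6, 43.2 and 46.8 for N = 66, 72 and 78, or about 39-46 after 5% loss to follow-up. Table 10's lower counts arise because it assumes a large benefit in the cetuximab arm.

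**3. Approximate power.** For a continuous covariate, the noncentrality is D × (ln HR per SD)². Cutting a normal covariate at c, with proportion p on one side, multiplies it by φ(c)²/[p(1 − p)]. At 50/50 this is 0.3989²/0.25 = 0.637; at 70/30 it is 0.576, at 80/20 0.490 and at 90/10 0.342. Three groups retain 0.78-0.81, but on 2 degrees of freedom.

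Example with D = 42 and HR 1.5 per SD:

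- Continuous: 42 × 0.4055² = 6.90, root 2.63, power Φ(2.63 − 1.96) = 75%.
- 50/50 cut: 6.90 × 0.637 = 4.40, root 2.10, power Φ(2.10 − 1.96) = 55%.

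With D = 28 the same steps give 57% and 40%. Three groups give 38-55% over D = 28-42.

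**4. Simulation.** Settings: exponential survival, 2-year OS 40%, 5% loss, 24-month follow-up, normal covariate with log-linear effect, 2000 runs per setting (standard error of a power estimate at most about 1.1 points). Power at HR 1.5 per SD:

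| N | Continuous | 50/50 | 65/35 | 75/25 | Three groups (25/50/25) |
|---|---|---|---|---|---|
| 66 | 69% | 49% | 43% or 52% | 36% or 51% | 50% |
| 72 | 73% | 53% | 46% or 55% | 37% or 54% | 53% |
| 78 | 77% | 55% | 49% or 58% | 43% or 56% | 57% |

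For uneven cuts, the first figure has the smaller group at low risk and the second has it at high risk. The loss here runs from 69 − 52 = 17 to 73 − 37 = 36 points. Including HR 1.35, where the loss can be smaller, the range is roughly 12-35 points once simulation error is allowed for.

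**5. Sensitivity to the assumptions.**

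- HR 1.2 per SD: loss about 4-11 points, because no test has much power.
- HR 2.0 per SD: loss about 3-26 points, largest for an uneven cut with a small low-risk group.
- A 90/10 cut at HR 1.5, by the formula in step 3: loss 33-41 points.
- A true step exactly at a 50/50 cut (N = 78, HR 2): the grouped test has 64% power and the linear term 45%, so the sign reverses.
- One U-shaped example: the linear term had 6% power, against 34-46% for three groups.

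**The case against.** The strongest objection is that these analyses carry little weight in the trial. Sections 3.1, 3.2, 8.2.1 and 8.2.2 list no prognostic-factor objective or variable. Section 8.4 rests the conclusion on the OS rate with its confidence interval, the reference arm and toxicity. The treatment hazard ratio comes from a univariate Cox model. All of this stands. A reader might infer that a planned conclusion of the trial is weakened, or that coarse grouping leaves the treatment effect confounded. The documents support neither reading, because the treatment comparison does not use these factors.

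The size of the loss rests on assumptions. The documents give no distribution, split or effect size. Eligibility truncates haemoglobin at 10.0 g/dL and admits patients over 75 only with KPS of at least 80 (Section 4.2.2), so an untruncated normal covariate is an idealisation. Three unordered groups can detect a non-monotone effect that one linear term misses. The cut points are also prespecified, not chosen from the data. These points stand; they limit the claim without removing it.

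Lastly, few deaths and the P < 0.05 entry rule cause much of the missed-factor risk. At HR 1.5 per SD with 28-42 events, even the continuous test misses a true factor in 25-43% of trials. With a 50/50 cut it is 45-60%. Grouping adds to the risk but is not its only source, and recoding does not remove the entry rule.

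**Conclusion.** The point holds as a low-priority improvement to the exploratory prognostic analyses. Under a log-linear effect, grouping loses power and raises the risk that a true factor fails the univariate screen. The loss is roughly 12-35 points for HR 1.35-1.5 per SD, given a normal covariate, 66-78 patients and about 39-46 deaths by 2 years.

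A reader might go further and conclude that the plan loses a fixed 15-35 points, or that true factors will be dropped. The documents do not support that. The loss depends on the effect size, the split, which group is at high risk, and the shape of the effect; it becomes a gain when a real threshold lies at the cut. Omission of a true factor is a raised risk, not a certain result. The primary endpoint and the treatment comparison are unaffected.

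**What to change.** In Section 8.3.1 and the synopsis:

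- Make the main prognostic test for age, tumour length and haemoglobin a Cox model with each as a continuous term (for example per 10 years, per cm and per g/dL), and carry that form into the multivariate model.
- Add one simple, prespecified check for non-linearity.
- Keep the stated groups for the Kaplan-Meier plots and descriptive rates, and report the grouped log-rank tests as a sensitivity analysis.

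The cost is a change of wording. No new data are needed provided tumour length is recorded in cm. If only the category is held, the change applies to age and haemoglobin alone. The downside is that a linear term is weaker when the true effect is a threshold at the cut or is non-monotone, which the non-linearity check and the grouped sensitivity analysis are there to cover.

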8.2 Target variables

8.2.1 Primary variables

For quantification of efficacy the primary objective is the 2-year overall survival.

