8.3.3 Rationale for the application of a randomized phase II design

The present trial is designed as a randomized phase II study which aims at estimating the therapeutic efficacy of the experimental targeted regimen including the EGFR antibody in relation to the standard combination. The OS rate after 2 years is chosen as primary efficacy endpoint.

The estimation of the efficacy rate of the experimental cetuximab regimen is to be based on an explorative pilot study, since immediate embarking on a large scale comparative efficacy trial would not be acceptable from the point of view of resources. Moreover, this would induce ethical objections, as it does not seem to be justifiable to expose a large number of patients to an experimental approach without any exploratory indications of an improved risk-benefit ratio.

In this situation, a randomized phase II trial with a standard treatment control group proves to be an appropriate research design in order to achieve a valid efficacy estimation. This type of cancer study design is propagated since the early 1980s, especially by representatives of the National Cancer Institute [48]. The key idea of randomizing already in the phase II of the treatment development offers the opportunity to reduce some of the result variability which is typically encountered in phase II trials, especially caused by patient selection phenomena and investigator bias. Thus, with a randomized control group at hand, differences obtained for the two treatments will more likely represent real differences in efficacy rather than differences in patient selection, clinical evaluation, and other factors, since these factors will be handled in similar fashion for both arms of the study. The purpose of randomized phase II designs is not a formal, rigorous comparison of two or more treatment arms, but rather a reduction in certain sources of variability that afflict conventional phase II trials and their comparison across studies. Moreover, this design offers the additional advantage, that the trial may immediately be expanded into a phase III trial including the patients already randomized, if the results of the experimental group(s) are considered to be promising.

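### Below the primary OS comparison, one unadjusted P < 0.05 verdict covers 36 prognostic-factor tests and the arm comparisons of PFS, MFS and LC, so chance findings labelled significant are likely; a wording change is enough

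*Combined protocol and SAP*

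**What the plan says.** Section 8.2.1 ranks the endpoints: "For quantification of efficacy the primary objective is the 2-year overall survival". Section 8.2.2 lists PFS, loco-regional control (LC) and metastases-free survival (MFS) as secondary.

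The testing rule is in Section 8.3.1 and is repeated in the synopsis under statistical methods. Its scope is set by "OS, PFS, MFS and LC are calculated for both treatment groups and for several potential prognostic factors with the Kaplan-Meier method". Nine factors follow: age, KPS, tumor location, tumor length, histology, grade, T-stage, N-stage and hemoglobin. The rule is "Differences between the Kaplan-Meier curves are evaluated with the log-rank test. Results are considered significant if" P < 0.05. The next step is "Potential prognostic factors found to be significant in the univariate analysis, are evaluated in a multivariate analysis performed with the Cox proportional hazard model".

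Three other places bear on the point:
- Section 8.3.3 describes the intent: "The purpose of randomized phase II designs is not a formal, rigorous comparison of two or more treatment arms".
- Section 8.3.4 treats gender, a tenth factor, differently: "the statistical evaluation analyses with respect to gender related differences will be presented in a descriptive manner".
- Section 8.4 gives detectable hazard ratios for the OS arm comparison at "80% power and a two-sided significance level of 0.05", and bases the trial's conclusion on the OS rate with its confidence interval, the reference-arm findings and toxicity.

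No section gives a testing order, an alpha split or any other error control for the comparisons below OS.

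**The concern.** A significance verdict is attached to 9 × 4 = 36 factor tests and to three secondary arm comparisons, each at 0.05, in a trial now expected to have 66 to 78 patients. With that many tests, some will cross the threshold by chance. A univariate hit is also the entry ticket to the Cox model, so a chance finding can reappear as a multivariate result.

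Two things are at stake. The report may name a prognostic factor as significant when it is noise. It may also report a significant cetuximab effect on PFS, MFS or LC beside a null OS result, and the plan does not say how to read that combination.

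**Working it through.** **Inputs from the documents.** Threshold 0.05 per test (8.3.1); two-sided, as stated in 8.4 for the OS arm comparison and assumed here for the factors. Four endpoints and nine factors (8.3.1). Total sample size 66–78 and 5% loss to follow-up over two years (8.4).

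**Inputs assumed.** The correlation among the four endpoint tests; in the simulation, also the event hazards and factor splits. The documents give none of these.

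**The plan's own figure.** The documents state no familywise error rate. The only figures tied to the 0.05 level are in Table 10. Events = 4(z₀.₉₇₅ + z₀.₈)² / (ln HR)², with HR = ln S(cetuximab) / ln S(control). First row: HR = ln 0.6314 / ln 0.30 = 0.382; events = 4 × 7.849 / 0.926 = 33.9, so 34 as printed. Eight of nine rows match; the ninth (2 × 36, 35%) gives 34 against 35. The stated level thus belongs to the OS arm comparison, and that calculation is sound.

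**Factor tests, analytic bounds.** Let p₁ be the chance that one null factor reaches P < 0.05 on at least one of four endpoints. For nine independent null factors the chance of at least one hit is 1 − (1 − p₁)⁹.

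| Endpoint correlation | p₁ | Nine null factors | Five null factors |
|---|---|---|---|
| 1 (one test per factor) | 0.050 | 37% | 23% |
| 0.8 | 0.114 | 66% | 45% |
| 0.5 | 0.156 | 78% | 57% |
| 0 (1 − 0.95⁴) | 0.185 | 84% | 64% |

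The last column, 1 − (1 − p₁)⁵, covers the case where KPS, histology, T-stage and N-stage, which underlie the randomization strata, have real effects.

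**Factor tests, simulation.** Null trials with n = 72, the four endpoints generated from one course of local progression, metastasis and death, independent factors, 3,000 runs per scenario. At least one of 36 tests has P < 0.05 in about 66–68% of trials with fast death after progression, 75–77% in the base case and 82% with slow death after progression. With only five null factors the figures are 46%, 56% and 61%. About 2 of the 36 tests are falsely significant on average (36 × 0.05 = 1.8 in theory). OS alone (nine tests) gives 38–41%.

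**Arm comparisons.** For PFS, MFS and LC, P(at least one < 0.05) is 9.8% at correlation 0.8 and 12.6% at 0.5, with a ceiling of 1 − 0.95³ = 14.3%. The simulated scenarios give 9%, 11% and 13%.

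**The case against.** The case against a serious finding is good, and much of it stands.

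- A reader might infer that the trial has no hierarchy of endpoints. The documents do not support that: 2-year OS is the sole primary variable and the others are secondary. What is missing is error control below OS. The extra tests do not change the error rate of the OS comparison, and Section 8.4 lets no prognostic-factor, PFS, MFS or LC P value into the conclusion.
- A reader might want a single false-positive rate of about three in four. The documents do not fix one. It depends on endpoint correlation and on a global null that the stratification itself makes doubtful. Correlation between factors would lower it: if all 36 statistics were equally correlated at 0.5 the figure would be 55%, and at 0.8, 27%. That model treats tests of different factors as being as closely related as tests of one factor on different endpoints.
- A reader might infer that the reason for making gender descriptive applies equally to the nine factors. It does not. Section 8.3.4 rests on low power within each gender subgroup; the nine factors are whole-cohort comparisons, and power is a different matter from multiplicity.
- The factor figures count univariate hits. How many would survive the Cox model was not computed.
- The study is declared explorative throughout. This lowers the severity but does not remove the point: Section 8.3.1 still attaches a verdict to each test, and an exploratory aim argues for dropping that verdict.

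**Conclusion.** The point holds as a minor one. Under a global null, the rule as written would call at least one prognostic factor significant in about 67–82% of trials, within bounds of 37–84% for independent factors. If the four factors tied to stratification are truly prognostic, the chance falls to about 45–58% (61% in the slow-death scenario), roughly even odds. At least one of PFS, MFS and LC would separate the arms at P < 0.05 in about 10–13% of trials with no treatment effect, a modest excess over 5%. These ranges rest on two-sided tests, independent factors and assumed endpoint correlations, roughly 0.5–0.8 or as implied by the simulated disease course. The primary OS comparison and the go/no-go conclusion are untouched.

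**What to change.** In Section 8.3.1 and the matching synopsis text:

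1. Restrict the P < 0.05 significance rule to the between-arm OS comparison.
2. Report the arm comparisons of PFS, MFS and LC as exploratory: hazard ratios with 95% confidence intervals and nominal P values. Section 8.4 already plans a hazard ratio with its interval for OS.
3. Report all prognostic-factor analyses, univariate and multivariate, as hypothesis-generating hazard ratios with 95% confidence intervals and no significance verdict.

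No fixed testing order for the secondary endpoints is proposed, because the documents give no basis for one. The change needs no new patients or data. Its cost is that individual prognostic factors and secondary endpoints can no longer be called significant in the report.
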